## **Clinical and Urgent Colonoscopy Outcomes using the Pure-Vu® Cleansing System in Hospitalized Patients with Lower Gastrointestinal Bleeding: A Single-Center Prospective Pilot Study**

### **BACKGROUND:**

Acute lower gastrointestinal bleeding (LGIB), while generally defined as gastrointestinal bleeding distal to the ligament of Treitz, can be categorized into small bowel and colorectal bleeding, two sites with distinct presentations as well as diagnostic and management options (1). Acute LGIB secondary to a colorectal source usually presents with sudden onset hematochezia with or without acute blood loss anemia and hemodynamic instability, and usually leads to multiple invasive procedures and hospitalizations. It accounts for up to one-third of all hospitalizations related to GIB (2). The current guidelines recommend urgent colonoscopy to be performed within 8 to 24 hours of presentation and after adequate colon preparation to improve visualization and diagnostic/therapeutic yield (1). While studies looking at optimal timing of colonoscopy are limited for patients with acute LGIB, a study comparing 48 patients with diverticular bleeding who underwent colonoscopy after rapid polyethylene glycol (PEG) preparation and within 12 hours of presentation with endoscopic hemostasis compared to 73 controls without endoscopic hemostasis, found a significant improvement in outcomes in the group that underwent hemostasis, including bleeding (0% vs. 53%) and hospital length (median of 2 days vs. 5 days) (3). In another RCT of 100 patients presenting with LGIB, colonoscopy within 8 hours of presentation after rapid preparation lead to a more definite diagnosis compared to patients who underwent elective colonoscopy within 96 hours of presentation (4). Urgent colonoscopy however requires the rapid administration of a large volume bowel preparation over 3-4 hours until the rectal effluent is clear (1). Purge preparation can be challenging in critically ill patients and frequently requires the placement of a nasogastric tube for administration of the preparation which could place the patient at risk of aspiration, poor tolerance, and rarely, electrolyte imbalances (1). Moreover, bleeding can

subside while awaiting resuscitation and bowel preparation prior to endoscopic intervention, which could lead to a decreased diagnostic and therapeutic yield. The guidelines recommend against unprepped colonoscopy due to poor visualization and increased perforation risk (1). A pilot study looked at the effect of “hydroflush colonoscopy” in acute LGIB with minimally prepped colons (tap water enema without oral preparation). “Hydroflush colonoscopy” was defined as colonoscopy using a combination of a water jet pump irrigation and a mechanical endoscope suction device (BioVac direct suction device). Out of the 12 patients included, the cecum was reached 69% of the time and endoscopic visualization was found to be adequate to find the source of bleeding in all procedures (5). The Pure-Vu® System (MotusGI Ltd.), a novel Food and Drug Administration (FDA) 510k cleared intra-procedural cleansing device, has been recently introduced. The Pure-Vu® System integrates with the colonoscope and generates a pulsed vortex mixture of water and air in order to remove debris and is active at the time of cleansing to evacuate colonic contents simultaneously (6). Its effectiveness has been studied in colonoscopies requiring minimal preparation regimens with excellent and safe results (7,8). A multicenter European feasibility study looked at 47 patients referred for colonoscopy who received a limited bowel preparation and found significant improvement in the proportion of patients with adequate preparation, with a median Boston bowel preparation score (BBPS) increased from 3[0-5] to 9 [8-9] (8). The REDUCE trial (9), another multicenter, single-arm study, was the first trial to study Pure-Vu® in the inpatient setting, which enrolled 95 hospitalized subjects. Adequate bowel preparation improved from 38% (95% CI 28,49) to 96% (CI 90-99) in the evaluated segments. The mean BBPS improved from 1.74 in the left colon, 1.74 in the transverse colon, 1.5 in the right colon to 2.89, 2.91 and 2.86 respectively (p<0.001) (9).

## **HYPOTHESIS:**

The Pure-Vu® System can be effectively used as a cleansing device in patients admitted with acute LGIB to the intensive care unit and the regular nurse floor (RNF) bypassing the need to

administer an oral bowel preparation for adequate visualization and hence decreasing time to colonoscopy and improving diagnostic and therapeutic yield.

**PRIMARY OUTCOME:**

The primary outcome of the study will be the proportion of patients who achieve an adequate bowel preparation to identify bleeding lesions (i.e. BBPS $\geq$  2 in all 3 colonic segments, which will be determined by the endoscopist).

**SECONDARY OUTCOMES:**

Secondary outcome measures will include:

- Diagnostic yield defined as the identification of the source of bleed or adequate visibility to rule out a LGIB source
- Therapeutic yield defined as control of bleeding source through endoscopic interventions
- Re-bleeding rate defined as recurrent hematochezia/ bright red blood per rectum within 48 hours of the index colonoscopy with Pure-Vu® system
- Need for repeat colonoscopy within 48 hours of index colonoscopy using Pure-Vu® to control source of bleed
- Length of the procedure
- Endoscopist satisfaction
- Length of intensive care unit (ICU) stay (only applicable if subject had colonoscopy in the ICU)
- Length of hospital stay

## **METHODOLOGY:**

### **Study Design:**

This will be a single-center, single-arm feasibility study which will be conducted at our tertiary care center, Cleveland Clinic, Cleveland, Ohio, United States.

### **Study Population:**

Eligible patients will be hospitalized patients with acute LGIB undergoing urgent colonoscopy under monitored anesthesia care or conscious sedation.

### Inclusion criteria:

1. Hospitalized patients in the ICU or the RNF with acute LGIB (defined as maroon-colored stool or bright red blood per rectum with suspicion of acute blood loss anemia, and hemodynamically stable and/or stabilized at the time of procedure. Hospitalized patients include:
  - Patients who develop LGIB while admitted for different reasons
  - Patients transferred from an outside hospital for further management of acute LGIB
  - Patients admitted through the emergency room for management of acute LGIB
2. ≥22 years old (age cleared by the FDA for device use)
3. Undergoing urgent colonoscopy under general anesthesia or conscious sedation

Exclusion criteria:

Patients will be excluded if:

1. Suspicion for bowel obstruction/ stricture
2. Toxic megacolon or severe colitis (determined by degree of colitis on imaging and clinical condition including pain, fevers, abdominal exam, elevated inflammatory markers)
3. Active Diverticulitis
4. Confirmed COVID-19 positive
5. Patients with no capacity and unable to provide informed consent

**Variables to be collected and studied:**

- Patients Characteristics and Demographics:

Date of birth, gender, ethnicity, body mass index, American Society of Anesthesiologists classification, surgical history of the abdomen and pelvis.

- Admission Characteristics:

Hospital (CCF) admission date and time, presenting GI Bleeding symptoms (maroon-colored stool, bright red blood per rectum, abdominal pain, etc.), Baseline labs (if available) and labs at the time of LGIB development (hemoglobin, INR, platelet count), last dose of anticoagulation at time of colonoscopy, blood product transfusion

- Procedure Characteristics:

Date of colonoscopy procedure, type of scope used, type of oversleeve used, colonoscopy start time (scope in time), colonoscopy end time (scope out time), colonoscopy completion, reason for colonoscopy non-completion, segment reached if colonoscopy incomplete, desired segment if colonoscopy incomplete (ileum vs. cecum), cecal

intubation, time to cecal intubation, time for device assembly, sedation type, BBPS pre and post Pure-Vu® System, pathologies found and characteristics (including size, location, morphology, etc.), interventions performed and time spent on each intervention

- Follow up and Adverse event collection:

Adverse event (AE) occurring at the time of the procedure will be documented in the AE form. A follow up visit or call will be conducted 24-48 hours after the procedure. The patient will be interviewed by one of the study co-investigators or coordinator and if an adverse event (AE) is reported, the AE form will be completed.

Any adverse events related to the study will be immediately reported to the Institutional Review Board (IRB).

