### Anesthesia and Colonoscopy:

Patients will receive general anesthesia by the ICU or anesthesia team, or, conscious sedation (usually a combination of Fentanyl and Midazolam) by the endoscopist. The choice of sedation will be determined by the primary team, anesthesiologist and/or endoscopist.

Colonoscopies will be performed using Olympus CF-HQ190L and PCF-H190L colonoscopes. The choice of an adult or pediatric colonoscope will be left to the endoscopist's discretion. Each procedure will be performed by a senior gastroenterology fellow under the supervision of a gastroenterology attending. The endoscopy cart nurses will be trained to set up and trouble shoot the Pure-Vu® System. The gastroenterology fellow and attending will receive instructions and training of device use prior to use.

Cleansing success will be attained if a BBPS of  $\geq 2$  is achieved in all segments. Pre and post cleansing photo-documentation will be obtained as well photo-documentation of any bleeding lesion.

A colonoscopy using the Pure-Vu® System will be considered complete if the cecum is reached or bleeding site is found distal to the cecum. A colonoscopy will be considered "incomplete" if the endoscopist elects to stop the procedure for patient safety (patient intolerability, or hemodynamic instability) or technical difficulties. If the endoscopist cannot reach the cecum with Pure-Vu® due to technical difficulties, the endoscopist has an option to use a naked scope to attempt to complete the procedure. If the procedure is incomplete the patient will then undergo standard of care bowel preparation and standard colonoscopy. This will include having the patient consume a bowel preparation at least 4 hours prior to standard of care colonoscopy.

After the procedure, a follow up visit or call will be conducted to check in on the patient's wellbeing. If an adverse event is reported, the adverse event form will be completed and submitted to the IRB.

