### Data monitoring:

Data will be collected from the electronic medical record and managed using an IBM platform built by Motus and the Cleveland Clinic team.

Data collection forms including the case report forms, pre and post-procedure patient surveys, post-procedure endoscopist and nursing staff satisfaction surveys, adverse event forms will be completed as described above. The study coordinator will enter the data into the IBM platform. The data collection forms and questionnaires will be stored safely with the study coordinator in the DDSI department.

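### Re-bleeding is counted over 48 hours, but the only scheduled contact may fall at hour 24, so re-bleeding at home after discharge can be missed

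*Protocol*

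**What the plan says.** Under Secondary Outcomes, the protocol defines re-bleeding as "recurrent hematochezia/ bright red blood per rectum within 48 hours of the index colonoscopy" with the device. It gives a second outcome the same window: "Need for repeat colonoscopy within 48 hours of index colonoscopy" to control the source of bleeding.

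Under Variables to be collected and studied, the follow-up item states: "A follow up visit or call will be conducted 24-48 hours after the procedure". The patient is interviewed, and an adverse event form is completed if an event is reported. The Anesthesia and Colonoscopy section mentions the contact again without timing ("a follow up visit or call will be conducted to check in on" the patient's wellbeing). No later contact appears in the protocol.

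The Data monitoring section says "Data will be collected from the electronic medical record" but sets no time point for that review. The Case Report Form section says that the form will include the variables listed in the methodology. That list names neither re-bleeding nor repeat colonoscopy.

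**The concern.** The contact window ends where the outcome window ends. Only a contact at exactly hour 48 lets the patient report on the whole period; any earlier contact leaves part of it unasked. The stated purpose of the contact is wellbeing and adverse events, and no question on bleeding is named.

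The gap concerns patients who are both contacted and discharged before hour 48. Hematochezia is a symptom. If it happens at home and the patient does not return to this center, the chart has no entry to find. A repeat colonoscopy at another hospital could also be missed, though less often.

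Early discharge is plausible. The protocol requires no minimum stay, and its Background cites a median hospital stay of 2 days in patients with diverticular bleeding who had endoscopic hemostasis. If that stay is counted from admission (an assumption), about half had left by hour 48 of admission, which comes before hour 48 after colonoscopy.

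Missed events can only lower the observed rates. Among early discharges, patients called at hour 24 and at hour 48 would be pooled as if observed for equally long.

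**Working it through.** The protocol gives no expected re-bleeding rate and no figure for discharge before hour 48, so there is no figure of its own to reproduce. The check has four steps.

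**1. Uncovered time.** Inputs: outcome window 0-48 h (Secondary Outcomes) and contact at hour c between 24 and 48 (Variables to be collected). Uncovered share = (48 − c)/48.

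| Contact hour | Hours left | Share of window |
|---|---|---|
| 24 | 24 | 50% |
| 30 | 18 | 37.5% |
| 36 | 12 | 25% |
| 42 | 6 | 12.5% |
| 48 | 0 | 0% |

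**2. Share of 48-hour events missed.** Let f be the share of post-contact events that the chart does not capture. Among patients who re-bleed, assume an exponential time to re-bleed, F(t) = 1 − exp(−t·ln 2/median), with median 12, 24 or 48 h.

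- Contact at hour 24: missed share = f × [1 − F(24)/F(48)]. For a median of 24 h, F(24) = 0.50 and F(48) = 0.75, so 1 − 0.50/0.75 = 33.3% at f = 1.
- Contact times spread uniformly over 24-48 h: missed share = f × [1 − mean F(c)/F(48)]. For a median of 24 h, mean F(c) = 0.639, so 1 − 0.639/0.75 = 14.8% at f = 1.

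| Median time to re-bleed | Hour-24 contact: f = 1 | f = 0.5 | f = 0.25 | Uniform contact: f = 1 | f = 0.5 | f = 0.25 |
|---|---|---|---|---|---|---|
| 12 h | 20.0% | 10.0% | 5.0% | 7.8% | 3.9% | 1.9% |
| 24 h | 33.3% | 16.7% | 8.3% | 14.8% | 7.4% | 3.7% |
| 48 h | 41.4% | 20.7% | 10.4% | 19.5% | 9.8% | 4.9% |

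At f = 0 every entry is 0. The f = 1 columns, with no chart capture at all, are an upper bound on f and are not realistic for a population of inpatients.

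**3. Sensitivity to the timing model.** Assume instead a constant hazard in all patients, set to give a true 48-hour rate of 20%. Then the 24-hour rate is 1 − (1 − 0.20)^0.5 = 10.56%. At f = 1 the missed part is 20 − 10.56 = 9.44 percentage points, or 9.44/20 = 47% of events. So 41% is not a strict ceiling. The same model gives 24% at f = 0.5 and 12% at f = 0.25.

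**4. In this trial.** N = 20 (Sample size calculation), so each missed event moves the rate by 1/20 = 5 percentage points. Suppose 4 of 20 patients truly re-bleed (assumed) and all contacts fall at hour 24. Expected missed events = 4 × missed share, and observed rate = (4 − missed)/20. Ranges cover medians of 12 to 48 h.

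| f | Missed events, exponential | Observed rate | Missed events, constant hazard | Observed rate |
|---|---|---|---|---|
| 1 | 0.80-1.66 | 11.7-16.0% | 1.89 | 10.6% |
| 0.5 | 0.40-0.83 | 15.9-18.0% | 0.94 | 15.3% |
| 0.25 | 0.20-0.41 | 17.9-19.0% | 0.47 | 17.6% |

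For comparison, the exact (Clopper-Pearson) 95% confidence interval for 4/20 is 5.7% to 43.7%.

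**The case against.** The strongest reply is that the gap is narrow. Every participant is an inpatient at the index colonoscopy. Some are in intensive care, and some bled during an admission for another reason. The medical record is a named data source, and length of stay is an outcome, so records must be followed to discharge. An event is lost only if the patient is contacted before hour 48, is discharged before hour 48, bleeds after both, and leaves no trace at this center. This stands, and it is why f should be well below 1.

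The early-discharge evidence is also selective. The same Background sentence gives a median of 5 days for controls without hemostasis, and this trial is not limited to patients who receive it. That stands too: the share discharged before hour 48 is unknown.

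The variable list is clearly not exhaustive. It omits the discharge date although length of stay is an outcome, so its silence on re-bleeding does not show that re-bleeding goes unrecorded. A patient may also report bleeding as an adverse event. Both points are fair, but neither helps with bleeding that starts after the contact.

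The size rests on assumptions. The exponential model makes sense only among patients who re-bleed, and a different model moves the range, as shown above. The figures are therefore illustrative. Finally, this is a descriptive secondary outcome in a 20-patient single-arm pilot, which limits the weight of the point but does not remove it.

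**Conclusion.** The concern holds. The protocol sets a contact rule that can leave up to half of the outcome window unasked, and chart review alone cannot recover bleeding at home. This is not detail that a statistical analysis plan could supply, because events never asked about cannot be recovered at analysis.

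The effect is one-directional: it lowers the re-bleeding rate and, to a lesser degree, the repeat-colonoscopy rate. It arises only in patients contacted and discharged before hour 48. With an hour-24 contact, the loss is about 5-12% of 48-hour events at f = 0.25 and 10-24% at f = 0.5, across the two timing models. It is zero if the chart captures everything. The values of f, the re-bleeding times and the 20% rate are assumptions.

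The expected shift is smaller than the sampling error with 20 patients, and the primary outcome (BBPS) is scored during the procedure and is unaffected. The change should still be made, because a larger sample would not remove the bias and the remedy is cheap. The case report form itself is not shown, so this is a gap in what the protocol fixes and not proof that events go unrecorded.

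**What to change.** Move the outcome contact to hour 48 or later, for example 48-72 hours after the procedure; an earlier safety check can stay. At that contact, ask directly about hematochezia in the 48 hours after the procedure and about any repeat colonoscopy, at this center or elsewhere. This is the change that closes the gap.

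Two supporting additions: state that the chart is reviewed through hour 48 for every patient, and record the date and time of each re-bleed and repeat colonoscopy, so that events after hour 48 can be excluded.

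The cost is one shifted call window, one sentence, and two case report form fields if they are not already there. The drawback is a slightly later call, more often after discharge. Clinical management does not change.

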**Definitions:**

Boston bowel preparation score:

The BBPS is a well validated tool used to describe the adequacy of a bowel preparation. It is applied upon withdrawal and after thorough cleaning and suctioning of each of the left colon (rectum, sigmoid colon and descending colon), transverse colon (including hepatic and splenic flexures) and right colon (ascending colon and cecum). Each of the 3 segments is then given a score as follows:

- 0 = Unprepared colon segment with mucosa not visualized due to solid stool that cannot be cleared.
- 1 = Areas of colonic mucosa seen, but other areas of the colon segment not well seen due to staining, residual stool and/or opaque liquid (residual fluid/ stool covering more than one-third of a colonic segment).
- 2 = Minor amount of residual fluid content, small fragments of stool and/or opaque liquid, but mucosa of colon segment seen well (contents covering less than one-third of a segment's mucosal surface).
- 3 = Excellent visualization of the colonic mucosa with no residual fluid or stool fragments.

In our study, we will be measuring the BBPS in each colonic segment before and after washing with the Pure-Vu® System. Endoscopists will be required to spend at least 3 minutes washing in each segment before assigning it a BBPS score.

Withdrawal time:

Withdrawal time is defined as the amount spent examining the colonic mucosa as the scope is being withdrawn from the cecum to the anus.

Acute blood loss anemia

Acute blood loss anemia will be defined as at least 1 gram drop in hemoglobin when compared to baseline.

Urgent colonoscopy

Urgent colonoscopy will be defined as colonoscopy performed within 24 hours of presentation

**Study Procedures:**

Identification of participants:

Patients admitted to CCF intensive care unit or RNF, with acute LGIB will have their chart reviewed by one of the study members to ensure eligibility and eligible patients will be invited to participate in the study. The patient will be introduced to the study and provided with the study information. Consent will be obtained from the patient the day of the procedure prior to any study activities. As previously mentioned, patients unable to provide informed consent will be excluded from the study.

Bowel preparation:

Enrolled patients will not receive any oral bowel preparation but will receive 2 tap water enemas approximately 30-60 minutes prior to the procedure, 15-20 minutes apart. Patients will be required to be *Nulla per Os* for at least 4 hours prior to the procedure to decrease aspiration risk with sedation.

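### The no-oral-preparation rule starts at enrolment: patients prepared before same-day consent are eligible, count toward the primary outcome, and are not identified on the case report form

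*Protocol*

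**What the plan says.** The Protocol's Hypothesis section states that the device bypasses the need to "administer an oral bowel preparation for adequate visualization". The rule meant to deliver this is in Study Procedures, Bowel preparation: "Enrolled patients will not receive any oral bowel preparation"; they are given two tap water enemas instead. Just above it, under Identification of participants: "Consent will be obtained from the patient the day of the procedure prior to any study activities".

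The inclusion criteria name three routes into the study. Two involve hospital care before the study team's contact: "Patients transferred from an outside hospital for further management of acute LGIB" and "Patients who develop LGIB while admitted for different reasons". There are five exclusions: suspected obstruction or stricture, toxic megacolon or severe colitis, active diverticulitis, COVID-19, and "Patients with no capacity and unable to provide informed consent". None mentions bowel preparation already taken.

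The section on variables to be collected includes the bowel preparation score (BBPS) before and after the device. It has no item for oral preparation, its product, amount or time. The Case Report Form paragraph under Database takes its content from that list.

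The Primary Outcome section counts every patient with BBPS of at least 2 in all three segments, whatever the baseline score or earlier preparation.

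**The concern.** The preparation rule looks forward and applies to people who are already enrolled. Enrolment follows consent, and consent comes on the day of the procedure. Oral preparation that another hospital or the primary team started beforehand is therefore outside the rule, and nothing in eligibility catches it.

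This is plausible on the protocol's own account: the Background describes a rapid oral purge over 3 to 4 hours as what urgent colonoscopy requires. A patient who has had one may reach BBPS of at least 2 more easily. The success would then be reported as adequacy achieved without oral preparation.

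The study has one arm, so no control group shares the contamination. Whenever prepared patients do better than unprepared ones, the bias favours the device. A later statistical analysis plan could not reliably separate such patients on a variable that was never collected.

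**Working it through.** **1. Does any other rule close the gap?**

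- *Exclusions.* Five are listed and none concerns prior preparation.
- *Time window.* Definitions says: "Urgent colonoscopy will be defined as colonoscopy performed within 24 hours of presentation". A purge takes 3 to 4 hours (Background), and the fast before the procedure is at least 4 hours (Bowel preparation). The sum is 3 + 4 = 7 to 4 + 4 = 8 hours, which fits within 24. Neither the window nor the fast screens out a prepared patient.
- *Outcome definition.* Neither the Primary Outcome section nor the cleansing-success definition under Anesthesia and Colonoscopy sets a condition on earlier preparation or baseline BBPS.
- *Data.* No listed variable records oral preparation. The only admission time listed is that of the study hospital, so time under care elsewhere is not captured for transfers.

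Nothing closes it.

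**2. How large could the effect be?**

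The sample size section gives 20 patients with no target rate or power behind it, so there is no stated figure to reproduce. What follows is illustration.

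Inputs:

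- n = 20 (Sample size calculation).
- Success rate in prepared patients: 96%, an assumption. It is borrowed from the inpatient study cited in the Background, where it is adequacy after the device in the evaluated segments. The protocol does not describe how those patients were prepared.
- Success rate in unprepared patients, p: 50% to 90%, an assumption.
- Number prepared before consent, k: unknown; 2, 4 and 6 are shown.

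Each patient contributes 1/20 = 5 points. The expected proportion is (k × 0.96 + (20 − k) × p)/20, so the lift over p is k × (0.96 − p)/20.

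For k = 4 and p = 0.50: (3.84 + 8.00)/20 = 0.592, a lift of 9.2 points. For k = 4 and p = 0.90: (3.84 + 14.40)/20 = 0.912, a lift of 1.2 points.

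| Assumed p | Lift, k = 2 | Lift, k = 4 | Lift, k = 6 |
|---|---|---|---|
| 50% | 4.6 | 9.2 | 13.8 |
| 60% | 3.6 | 7.2 | 10.8 |
| 70% | 2.6 | 5.2 | 7.8 |
| 80% | 1.6 | 3.2 | 4.8 |
| 90% | 0.6 | 1.2 | 1.8 |

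(Lift in percentage points.)

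For scale, the exact 95% interval for 16/20 is 56.3% to 94.3%. Every lift in the table is smaller than that sampling uncertainty, but the interval does not allow for a shift in one direction.

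**3. How much would the planned data reveal?**

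The same cited study gives 38% adequacy before the device. If that rate held for prepared patients here (again an assumption), the pre-device score would show about 38% of them as already adequate. The other 62% would start with an inadequate score, as an unprepared patient might. An adequate starting score would also not tell oral preparation from the effect of the enemas.

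**The case against.** The strongest reply is that the intent is plain. The sentence sits under Bowel preparation and, read with the hypothesis, describes the whole preparation for the study colonoscopy. Site staff may well treat earlier oral preparation as disqualifying. That is a fair reading of purpose, but neither the eligibility criteria nor the rule says it.

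A reader might infer that contamination would be undetectable and could not be removed. The documents do not support that. BBPS is scored by segment before washing, photographs are taken before cleansing, a study member reviews each chart before invitation, and data come from the electronic medical record. With 20 patients at one center, charts could be searched one by one. This stands, and it limits the point: detection would be partial, not absent. It does not remove the point, because no such search is planned, outside-hospital records may be incomplete, and the score cannot identify the cause of a clean colon.

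A reader might also infer that many patients would be affected. No section says how often preparation precedes consent; the window is limited, and the number could be zero. The shift depends on assumed rates, and this is a feasibility pilot with no stated success threshold to cross.

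Finally, how to report such patients is commonly left to a statistical analysis plan, and its absence here is no fault. Eligibility and case report form content, however, are fixed in this protocol.

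**Conclusion.** The point holds as a gap in eligibility and data capture. Followed as written, the protocol admits a patient given oral preparation for the current bleed before consent, counts that patient toward the primary outcome, and has no field that says so. The resulting bias is upward for the claim of adequacy without oral preparation, provided prepared patients do better than unprepared ones.

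Its size cannot be estimated from the documents. Four such patients in 20 would add about 1 to 9 points under the assumed 96% in prepared and 50% to 90% in unprepared patients; with none, there is no bias. Because it touches the study's central claim and costs little to close, it should be corrected. It does not show that the study's results would be invalid.

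**What to change.** Add to the exclusion criteria: oral bowel preparation received for the current bleeding episode before consent. Add one item to the procedure variables, and so to the case report form: oral preparation for this episode before consent (yes/no, product, amount, time).

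If the sponsor prefers to keep such patients, base the primary proportion for the hypothesis on patients without prior oral preparation, and show the others separately.

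The planned sample of 20 need not change. Exclusion costs slightly slower enrolment. Keeping them costs a slightly smaller primary denominator: with four such patients among 20 it would be 16, and each patient would then weigh 1/16 = 6.25 points instead of 5.
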